## Results

The data was collected from a total of 49 participants (23 females and 27 males), and was then processed and analyzed. Participants age ranged from 40 to 78 years old (mean age= 62.8 years old, SD= 8.01, SE= 1.145, median= 63.0, 95% CI= 60.51 – 65.12).

Table 1 demonstrates the descriptive statistics for continuous variables in this study including dentist evaluations of dentures, patients' satisfaction with dentures, and OHIP-EDENT scores among the participants of this study. Paired comparisons of carved and non-carved lower dentures showed that patient satisfaction with retention at function ( $P= .002$ ) and comfort during the use of carved lower dentures ( $P= .026$ ) were significantly higher than non-carved lower dentures (Table 1). Furthermore, the patients demonstrated a tendency to be more satisfied with denture retention at rest as well as during eating when used carved lower dentures in comparison to non-carved ones. This difference was not significant but was close to be significant ( $P= .052$ ,

Table 1). In addition, carved lower dentures were associated with lower OHIP scores (better impacts on oral health) than the non-carved lower dentures; however, the difference was not significant ( $P= .055$ , Table 1). Nevertheless, this tendency was confirmed by the Mann Whitney U test as a significant difference was found in the OHIP scores between carved and non-carved lower dentures ( $MWU= 887.0$ ,  $Z= -2.241$ ,  $P= .025$ ). The carved lower dentures were associated with lower OHIP scores indicating better impacts on oral health than the non-carved dentures.

Table 2 presents the distribution (frequencies and percentages) of redness, erosion, keratosis, ulceration, and denture fissuratum following the use of the tested complete denture designs during this study. Redness was the most observed mucosal change, 18.4% with non-carved dentures and 12.2% with carved dentures. No significant differences in mucosal changes were observed between carved and non-carved lower dentures ( $P> .05$ , Table 2).

The results showed that the dentists assigned better ratings for upper dentures in comparison to non-carved lower dentures regarding to denture retention ( $P= .004$ ) as well as denture support ( $P= .011$ ) (Table 3). In addition, patients assigned significantly lower pain scores for upper dentures than non-carved lower dentures ( $P= .008$ , Table 3). Also, patients reported higher satisfaction with upper dentures considering denture retention at rest ( $P= .035$ ), denture retention at function ( $P< .001$ ), and comfort during denture use ( $P< .001$ ) in comparison to non-carved lower dentures (Table 3). In contrast, no significant differences between upper dentures and lower carved dentures regarding any dentist ratings or patient satisfaction for any evaluated factor ( $P> .05$  Table 3).

Gender base variations showed that females were assigned higher dentist ratings for retention of non-carved lower dentures ( $P= .031$ ), stability of lower non-carved dentures ( $P= .003$ ), support of lower non-carved dentures ( $P= .014$ ), esthetics of lower carved ( $P= .007$ ) and

non-carved dentures ( $P= .001$ ), stability of upper denture ( $P= .035$ ), and esthetics of upper denture ( $P= .004$ ) (Table 4). Also, females reported more pain with lower carved dentures in comparison to males ( $P= .015$ , Table 4). In addition, females assigned higher satisfaction ratings regarding retention during function of lower non-carved denture ( $P= .015$ ), comfort of lower non-carved denture ( $P= .007$ ), retention at rest for upper denture ( $P= .007$ ), retention at function for upper denture ( $P= .002$ ), comfort of upper denture ( $P= .001$ ), and retention during eating with upper denture and lower non-carved denture ( $P= .045$ ) (Table 4).

Table 5 presents correlations between age, patient satisfaction, and OHIP scores. The results show that older patients were more comfortable with upper dentures than younger patients (Spearman Rho= 0.309,  $P= .031$ , Table 5). Also, higher pain scores were associated with higher OHIP scores (i.e. worse impacts) after using carved ( $P= .001$ ) and non-carved ( $P< .001$ ) lower dentures (Table 5). In addition, lower OHIP scores (i.e. better impacts) were associated with higher satisfaction with retention at rest, retention at function, denture comfort, general satisfaction with dentures, retention during eating, and retention during speaking after using carved or non-carved lower dentures ( $P< .05$ , Table 5). Besides, correlations between age and dentist rating of dentures showed that older participants were found to have better dentist ratings of retention (Sperman Rho= 0.402,  $P= .004$ ) and higher stability (Spearman Rho= 0.402,  $P= .003$ ) of upper dentures than younger participants.

A multiple linear regression analysis was used to identify the contribution of having the retromolar pad area carved or not, satisfaction ratings, and dentist evaluation of dentures towards the prediction of OHIP scores considering the confounding effects of gender and age (Table 6). Being a female, having lower dentist ratings of denture esthetics, and having more pain due to lower dentures were associated with higher scores of OHIP indicating worse oral health impacts

of the prosthesis ( $P < .05$ , Table 6). Being a female was associated with an increase of OHIP scores by 4 units ( $P = .007$ ). Also, for each decreased unit of dentist ratings of denture esthetics, the OHIP scores were increased by 2 units ( $P = .018$ ). Furthermore, for each increased unit of pain levels due to lower dentures, the OHIP scores were increased by 0.7 units ( $P = .020$ ) (Table 6).

Further multiple linear regression analyses were conducted to identify the contribution of having the retromolar pad area carved or not and dentist evaluation of dentures towards the prediction of patient satisfaction with different denture aspects considering the confounding effects of gender and age (Table 7). The results showed that carved lower dentures were associated with 1.144 times higher satisfaction with lower denture retention during function ( $P = .040$ , Table 7). **[name] please note that Being carved or not was significant predictor for retention of the denture during function.**

Besides, patients satisfaction with lower denture retention at rest was decreased by 0.053 unit for each year increase in the age ( $P = .027$ , Table 7). Also, being a female was associated with higher patient satisfaction with lower denture retention at rest ( $B = 0.970$ ,  $P = .033$ ), lower denture retention at function ( $B = 1.404$ ,  $P = .027$ ), lower denture comfort ( $B = 1.374$ ,  $P = .007$ ), general satisfaction with upper and lower dentures ( $B = 1.361$ ,  $P = .002$ ), and retention of upper and lower dentures during eating ( $B = 0.978$ ,  $P = .036$ ) (Table 7).

In addition, higher levels of perceived pain due to lower dentures were associated with lower levels of satisfaction with lower denture retention at rest ( $B = -0.184$ ,  $P = .032$ ), lower denture retention at function ( $B = -0.365$ ,  $P = .002$ ), lower denture comfort ( $B = -0.440$ ,  $P < .001$ ), general satisfaction with upper and lower dentures ( $B = -0.254$ ,  $P = .002$ ), retention of upper and lower dentures during eating ( $B = -0.320$ ,  $P < .001$ ), and retention of upper and lower dentures during

speaking ( $B = -0.235$ ,  $P = .005$ ) (Table 7). Furthermore, higher dentist ratings of lower denture stability (**[name] please note for the discussion that this could be explained by that stability is related to each of retention, support and occlusion**) was associated with higher patient satisfaction with lower denture retention at rest ( $B = 0.527$ ,  $P = .037$ ), lower denture retention at function ( $B = 0.958$ ,  $P = .005$ ), and lower denture comfort ( $B = 0.723$ ,  $P = .011$ ) (Table 7).

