The calculated sample size was 46 participants. A priori power analysis based on linear multiple regression test (G\*Power, version 3.1.9.7; Heinrich-Heine University) calculated the minimum sample size to be 46 participants. The calculation considered a significance level ( $\alpha$ ) of .05, a statistic power ( $1 - \beta$ ) of 0.8, and an effect size of 0.3. Extra participants were recruited to balance for participant drop outs and secure the required minimum sample size. Fifty participants were recruited for the study, and none of participants was lost during the investigation (drop out ratio was 0%). Therefore, 50 participants were finally recruited and completed the study, and had their data collected and analyzed.

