## Tables

**Table 1.** Descriptive statistics for continuous variables including dentist evaluations of dentures, patients' satisfaction with dentures, and OHIP-EDENT scores among the participants of this study (N= 50).

Variable	Descriptive statistics						Paired comparisons of NCLD and CLD		
	Mean	SD	Med	Min	Max	IQR	Z	P	
Dentist evaluation of dentures									
Retention of NCLD	8.02	1.882	8.5	2.0	10.0	2.8	-1.357	.175	
Retention of CLD	8.34	2.011	8.5	2.0	10.0	1.8			
Stability of NCLD	8.36	1.454	8.5	2.0	10.0	1.5	-1.906	.057	
Stability of CLD	8.63	1.642	9.0	1.0	10.0	1.0			
Support of NCLD	8.78	1.295	9.0	2.0	10.0	1.0	-1.053	.292	
Support of CLD	9.05	0.694	9.0	7.0	10.0	1.0			
Esthetic of NCLD	8.87	0.846	9.0	6.5	10.0	1.0	-.223	.824	
Esthetic of CLD	8.90	0.878	9.0	6.0	10.0	1.0			
Retention of upper denture	8.89	1.217	9.0	5.5	10.0	1.5			
Stability of upper denture	8.66	1.192	8.5	4.5	10.0	1.5			
Support of upper denture	9.21	0.707	9.5	7.0	10.0	1.3			
Esthetic of upper denture	8.90	0.835	9.0	7.0	10.0	1.0			
Patient satisfaction with dentures									
Pain due to NCLD	2.08	2.745	0.0	0.0	10.0	4.0	-1.901	.057	
Pain due to CLD	1.20	2.336	0.0	0.0	8.0	1.0			
Retention at rest of NCLD	8.06	2.313	9.0	2.0	10.0	3.0	-1.943	.052	
Retention at rest of CLD	8.67	2.025	9.0	0.0	10.0	2.0			
Retention at function of NCLD	6.33	3.085	7.0	0.0	10.0	5.0	-3.054	.002	
Retention at function of CLD	7.59	2.684	8.0	0.0	10.0	3.5			
Comfort of NCLD	7.18	2.796	8.0	0.0	10.0	4.0	-2.225	.026	
Comfort of CLD	8.00	2.415	9.0	0.0	10.0	3.0			
Insertion of NCLD	9.92	1.891	10.0	2.0	20.0	0	-.071	.943	
Insertion of CLD	9.84	0.514	10.0	8.0	11.0	0			
Pain due to upper denture	0.67	2.115	0.0	0.0	10.0	0			
Retention at rest for upper denture	8.84	1.724	9.0	2.0	10.0	1.0			
Retention at function for upper denture	8.41	1.848	9.0	3.0	10.0	3.0			
Comfort for upper denture	8.74	1.765	9.0	2.0	10.0	2.0			
Insertion for upper denture	9.80	0.456	10.0	8.0	10.0	0			
General satisfaction with upper and non carved lower dentures	7.88	2.304	9.0	0.0	10.0	2.8			
General satisfaction with upper and carved lower dentures	8.37	1.551	9.0	4.0	10.0	2.0			
Retention during eating with upper and non carved lower dentures	7.25	2.260	8.0	1.0	10.0	3.0	-1.944	.052	
Retention during eating with upper and	7.98	1.953	8.0	0.0	10.0	2.5			

carved lower dentures								
Smile and appearance of upper and non carved lower dentures	9.61	0.885	10.0	6.0	10.0	0.5	-.283	.777

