Smile and appearance of upper and carved lower dentures	9.65	0.694	10.0	7.0	10.0	0.5		
Retention during speaking with upper and non carved lower dentures	9.14	1.414	10.0	3.0	10.0	1.0	-.662	.508
Retention during speaking with upper and carved lower dentures	9.10	2.400	10.0	0.0	20.0	2.0		
OHIP scores								
OHIP scores before dentures	22.59	10.82	20.0	4.0	48.0	17.0		
OHIP scores after using NCLD	11.12	7.793	9.0	2.0	39.0	8.0	-1.916	.055
OHIP scores after using CLD	8.45	6.433	6.0	0.0	31.0	7.5		

NCLD= Non-carved lower denture, CLD= Carved lower denture, OHIP= Oral Health Impact Profile – 14, SD= Standard deviation, Med= Median, Min= Minimum value, Max= Maximum value, IQR= Interquartile range, Z= Z statistic using Wilcoxon signed ranks test, P= Two-tailed probability value.

**Table 2.** Distribution of redness, erosion, keratosis, ulceration, and denture fissuratum following the use of the tested complete denture designs in this study (N= 50).

Variables	Non-carved lower denture				Carved lower denture				Comparison between carved and non-carved dentures	
	No		Yes		No		Yes			
	Fre	%	Fre	%	Fre	%	Fre	%	Z	P
Redness	40	81.6	9	18.4	43	87.8	6	12.2	-0.837	.402
Keratosis	49	100.0	0	0	49	100.0	0	0	0	1.00
Erosion	48	98.0	1	2.0	47	95.9	2	4.1	-0.583	.560
Ulceration	48	98.0	1	2.0	49	100.0	0	0	-1.000	.317
Denture Fissuratum	49	100.0	0	0	49	100.0	0	0	0	1.00

Fre= Frequency, % = Percentage. Z= Z statistic using Wilcoxon signed ranks test, P= Two-tailed probability value.

Table 3. Paired comparisons of dentist and patient denture ratings between upper complete dentures and each tested design of lower dentures in this study (N= 50).

Compared pairs	Z	P
Dentist evaluation of dentures		
Retention of NCLD versus upper denture	-2.887	.004
Retention of CLD versus upper denture	-1.506	.132
Stability of NCLD versus upper denture	-1.343	.179
Stability of CLD versus upper denture	-.854	.393
Support of NCLD versus upper denture	-2.558	.011
Support of CLD versus upper denture	-1.165	.244
Esthetic of NCLD versus upper denture	-0.019	.985
Esthetic of CLD versus upper denture	-0.153	.879
Patient satisfaction with dentures		
Pain due to NCLD versus upper denture	-2.653	.008
Pain due to CLD versus upper denture	-1.178	.239
Retention at rest of NCLD versus upper denture	-2.104	.035
Retention at rest of CLD versus upper denture	-0.285	.775
Retention at function of NCLD versus upper denture	-4.149	.000
Retention at function of CLD versus upper denture	-1.831	.067

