Comfort of NCLD versus upper denture	-3.546	.000
Comfort of CLD versus upper denture	-1.700	.089
Insertion of NCLD versus upper denture	-0.688	.491
Insertion of CLD versus upper denture	-0.500	.617

NCLD= Non-carved lower denture, CLD= Carved lower denture, Z= Z statistic using Wilcoxon signed ranks test, P= Two-tailed probability value.

Table 4. Gender based differences of dentist ratings of the dentures, patient satisfaction with dentures, and OHIP scores among the study sample (N= 50).

Variable	Male		Female		Gender difference		
	Mean	SD	Mean	SD	MWU	Z	P
Age	61.07	6.821	64.95	8.968	204.0	-1.873	.061
Dentist evaluation of dentures							
Retention of NCLD	7.48	2.040	8.68	1.452	191.0	-2.153	.031
Retention of CLD	7.85	2.437	8.93	1.105	228.5	-1.401	.161
Stability of NCLD	7.83	1.647	9.00	0.831	153.5	-2.931	.003
Stability of CLD	8.33	1.896	9.00	1.205	213.0	-1.721	.085
Support of NCLD	8.43	1.517	9.21	0.797	176.5	-2.466	.014
Support of CLD	9.02	0.628	9.09	0.781	267.5	-.611	.541
Esthetic of NCLD	8.56	0.738	9.25	0.827	133.5	-3.370	.001
Esthetic of CLD	8.65	0.806	9.21	0.882	166.5	-2.691	.007
Retention of upper denture	8.63	1.276	9.21	1.087	209.0	-1.808	.071
Stability of upper denture	8.32	1.360	9.09	0.781	194.0	-2.107	.035
Support of upper denture	9.17	0.785	9.27	0.612	283.5	-.279	.780
Esthetic of upper denture	8.63	0.715	9.23	0.869	157.5	-2.861	.004
Patient satisfaction with dentures							
Pain due to NCLD	2.22	3.068	1.91	2.348	290.0	-.151	.880
Pain due to CLD	0.70	1.918	1.82	2.684	198.5	-2.428	.015
Pain due to upper denture	0.30	0.912	1.14	2.965	285.0	-.424	.672
Retention at rest of NCLD	7.33	2.801	8.96	0.999	207.0	-1.860	.063
Retention at rest of CLD	8.52	1.949	8.86	2.145	257.5	-.841	.400
Retention at function of NCLD	5.33	3.234	7.55	2.444	177.0	-2.430	.015
Retention at function of CLD	7.22	2.778	8.05	2.554	231.0	-1.353	.176
Comfort of NCLD	6.22	3.017	8.36	1.989	165.5	-2.682	.007
Comfort of CLD	7.82	2.419	8.23	2.448	255.0	-.871	.384
Insertion of NCLD	9.56	1.577	10.36	2.172	266.5	-1.008	.313
Insertion of CLD	9.82	0.623	9.86	0.351	294.0	-.094	.925
Retention at rest for upper denture	8.26	2.087	9.55	0.671	172.0	-2.687	.007
Retention at function for upper denture	7.67	2.019	9.32	1.086	150.5	-3.074	.002
Comfort for upper denture	8.00	2.057	9.64	0.581	148.0	-3.210	.001
Insertion for upper denture	9.70	0.542	9.91	0.294	246.0	-1.525	.127
General satisfaction with upper and non carved lower dentures	7.26	2.768	8.64	1.246	222.0	-1.536	.125

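### The SAP states 50 participants analysed with no drop-out, but its printed results come from 49 (27 men, 22 women)

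*SAP*

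**What the plan says.** The sample size paragraph under Statistical analysis reports that 50 people were recruited, that "none of participants was lost during the investigation (drop out ratio was 0"%), and then: "Therefore, 50 participants were finally recruited and completed the study, and had their data collected and analyzed". The Results section says "The data was collected from a total of 49 participants (23 females and 27 males"). The captions of Tables 1 to 7 all give 50, for example "OHIP-EDENT scores among the participants of this study (N= 50"). No exclusion is mentioned anywhere.

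Table 2 prints counts that do not sum to 50 ("Redness 40 81.6 9 18.4 43 87.8 6 12.2"), and the text repeats its percentages: "Redness was the most observed mucosal change, 18.4% with non-carved dentures and 12.2% with carved dentures".

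Table 1 lists 35 ratings. Three have maxima above 10: insertion of the non-carved denture (20), insertion of the carved denture (11) and retention during speaking with the carved denture (20). The other 32 stop at 10 or below. The document does not state the rating scale.

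**The concern.** The number analysed and the account of participants are basic facts of the report, and here three statements disagree: 50 analysed, 49 analysed, and a gender split that adds to 50. There are two explanations with different consequences. If 50 and 23 are misprints, the statistics stand and only wording changes. If a 50th participant completed the study but is absent from the tables, an exclusion is undisclosed. That matters in a paired comparison with several results near .05: OHIP .055, retention at rest .052, retention during eating .052 and comfort .026.

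The ratings above 10 are a separate matter. If they are entry errors, they feed into means, SDs and some regression models.

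**Working it through.** **Head count.** Each check uses printed figures and asks which n reproduces them.

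- *Table 2, redness.* 40 + 9 = 49 and 43 + 6 = 49. 9/49 = 18.4% and 6/49 = 12.2%, as printed; 50 would give 18.0% and 12.0%.
- *Age SE = SD/√n.* 8.01/√49 = 1.144 and 8.01/√50 = 1.133; 1.145 is printed.
- *OHIP, carved against non-carved, Mann-Whitney U = 887, printed Z = −2.241* (the test for which the Results say "a significant difference was found in the OHIP scores between carved and non-carved lower dentures"). Untied Z = (U − n₁n₂/2)/√(n₁n₂(n₁+n₂+1)/12). This is −2.227 for 49 v 49 and −2.502 for 50 v 50. A tie correction can only raise |Z|, so 50 v 50 is impossible.
- *Table 4, same rule over 39 rows.* Rows whose printed |Z| is below the untied value: 0 with 27 men and 22 women, 34 with 27/23, 17 with 26/23. Example, retention during eating with the carved denture, U = 295, printed −.041: untied −.040, −.302 and −.080 respectively.
- *Table 4, women's means.* Assuming whole-number patient ratings and OHIP scores (tolerance .006), all 26 means are possible with 22 women and only 3 with 23. In "Retention at function of NCLD 5.33 3.234 7.55 2.444 177.0", 166/22 = 7.55, but 173/23 = 7.52 and 174/23 = 7.57.
- *Weighted means against Table 1.* The same row gives (27 × 5.33 + 22 × 7.55)/49 = 6.327, and 6.351 with 27/23; Table 1 prints 6.33. No row of 39 is off with 27/22; 15 are off with 27/23 (tolerance .01, and .05 for age).
- *Table 5.* rho = .309 gives P = .0307 at n = 49 and .0290 at n = 50; .031 is printed. rho = −.276 gives .0549 and .0524; .055 is printed.
- *Table 6 constant.* CI half-width/SE = (90.430 − 36.118)/2/13.648 = 1.9897, with a rounding range of 1.98963 to 1.98985. With 16 predictors, 98 records leave 81 df (t = 1.98969, inside); 100 leave 83 df (1.98896, outside).
- *Table 7 constants.* With 8 predictors, 98 records leave 89 df and 100 leave 91. The rest, comfort, general, eating and speaking models fit 89 and exclude 91; insertion and smile fit both.

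**One model that does not fit.** For the Table 7 retention-at-function constant, (13.273 + 4.249)/2/4.410 = 1.98662, range 1.98628 to 1.98696. That fits 90 or 91 df, and just misses 89 (1.98698). Its SEs are also not a constant multiple of the comfort model's: the ratio is 1.251 to 1.252 for the constant but 1.201 to 1.209 for stability. Other records or other predictors could explain this, so the model counts neither for 49 nor for 50. It holds the only significant carved term in Tables 6 and 7 (P = .040).

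**If a 50th record exists.** Give it the largest paired difference of all, in either direction, with m untied non-zero differences at present. The new |Z| is (|Z|·sd(m) ± (m+1)/2)/sd(m+1), where sd(m) = √(m(m+1)(2m+1)/24).

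| Outcome | Printed P | m = 25 | m = 49 |
|---|---|---|---|
| OHIP | .055 | .032 to .139 | .036 to .106 |
| Comfort | .026 | .015 to .077 | .016 to .055 |
| Retention at function | .002 | .001 to .011 | .001 to .006 |

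**Ratings above 10.** The women's mean for insertion of the non-carved denture gives 10.36 × 22 ≈ 228, above the 220 possible on a 0 to 10 scale. The women's SD for speaking with the carved denture is 3.274; on 0 to 10 with mean 9.36 and n = 22 the largest possible is 2.26. Neither 20 can be a man's: 26 × 1.577² = 64.7 is below (20 − 9.56)² = 109.0, and 26 × 1.368² = 48.7 is below (20 − 8.89)² = 123.4.

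The 20s are in the Table 7 outcomes. B × SD(gender)/Beta recovers the outcome SD: .498 × .500/.181 = 1.376 for insertion (1.379 with the 20; 0.906 with values above 10 set to 10, assuming one 11) and .702 × .500/.179 = 1.961 for speaking (1.960 and 1.618). One value supplies (20 − 9.88)²/184.5 = 56% of the insertion sum of squares and (20 − 9.12)²/372.5 = 32% of the speaking sum of squares.

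**The case against.** The printed P values already belong to 49 people and the Results section prints 49, so the likeliest remedy is a correction of wording and captions. The range for a missing record assumes the most extreme difference of all, without ties. Both remarks are fair: the range is a bound, not an expectation, and no change in a result has been shown. Even so, the stated analysed number is wrong for these results and the claim of no drop-out is left unsupported. Only source records can tell a misprint from an omitted participant.

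Table 3 prints only Z and P, so its n cannot be derived, and the misfit of the retention-at-function model rests on third-decimal rounding in one row plus the uneven SE ratios. Both limits stand. They call for an explanation of that model, and they do not weaken the other checks.

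The ratings above 10 have a different cause and remedy, and without a stated scale they are a strong inference rather than a proven error. That stands, so they are kept as a data query and add nothing to the weight of the main point.

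**Conclusion.** The concern holds. The printed results come from 49 participants, 27 men and 22 women. The stated 50 analysed, the 23 females and the captions giving 50 do not match them. Table 2, the age SE, the OHIP Mann-Whitney test, Table 4, Table 5 and Table 6 agree on this; only the whole-number check needs an assumption about the data. The error is one of accuracy and participant accounting, not of power, since 49 exceeds the planned 46. If a record was omitted, OHIP and comfort could cross .05 in the worst case, while retention at function stays significant.

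For the ratings, no significant carved-versus-non-carved result uses an item with a value above 10. Two significant Table 7 terms should not be relied on until the values are checked: support on insertion (P = .038, reported in the table only) and pain on speaking (P = .005, one of six pain associations in the text, the other five on unaffected outcomes). The coefficients cannot be recomputed without the raw data.

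**What to change.** 1. Reconcile the head count with source records. Then either include the 50th record and re-run all tables, or state that 49 (27 men, 22 women) were analysed and why.
2. If 49 stands, correct the number of females, the statement that 50 were analysed and the table captions. If a participant was lost or excluded, correct the drop-out statement as well.
3. State the records and predictors behind the Table 7 retention-at-function model, and re-run it with the predictors listed.
4. As a separate query, state the rating scale and check the values above 10 against the source forms. If they are errors, correct them or set them to missing. Then re-run the insertion rows of Tables 1 and 3 to 5, the speaking rows of Tables 1, 4 and 5, the Table 6 model, and the Table 7 insertion and speaking models.

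The cost is a head-count check, a query on a few forms (both 20s are in women's records), text corrections and a re-run of existing output. No new data are needed.

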### **Statistical analysis:**

The SPSS computer software (IBM SPSS Statistics v21.0; IBM Corp., USA) was utilized for the statistical analysis of the collected data in this study. The significance of the conducted statistical results was considered at two tailed  $\alpha$  of .05. Normal distribution of the data was tested utilizing the Shapiro-Wilk test and the skewness test considering skewness z-score threshold values range from -3.29 to +3.29. All the continuous variables were not normally distributed, except for age and OHIP scores before treatment. Descriptive statistics for normally distributed continuous variables (age and OHIP scores before treatment) included the mean, standard error, standard deviation, median, maximum value, minimum value, and confidence intervals. Meanwhile, descriptive statistics for the non-normally distributed continuous variables included the mean, standard deviation, median, interquartile range, minimum value, and maximum value. Categorical variables in this study (presence of redness, erosion, keratosis, ulceration, and denture fissuratum) were presented as frequencies and percentages.

The Wilcoxon Signed Ranks test was used to test paired differences in satisfaction ratings, dentist's evaluations, and OHIP-EDENT scores after using carved and non-carved lower dentures. The Mann Whitney U test was utilized to identify differences in satisfaction ratings, dentist's evaluations, and OHIP-EDENT scores between genders. Spearman's Rho rank correlations were used to identify the correlations between satisfaction ratings, dentist's evaluations, and OHIP-EDENT scores. Associations between identification of lesions following denture use (presence of redness, erosion, keratosis, ulceration, and denture fissuratum) and having the retromolar pad area of the lower denture carved or not were tested via Fisher's Exact test.

The multiple linear regression analysis was used to identify the contribution of having the retromolar pad area carved or not, satisfaction ratings, and dentist evaluation towards the prediction of OHIP-EDENT scores considering the confounding effects of gender and age.

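### The paired carved versus non-carved comparisons in Table 1 give only a signed-rank Z and P, with no paired difference or interval, and results just above .05 are described unevenly

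*SAP*

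**What the plan says.** The SAP, Statistical analysis, fixes the threshold ("The significance of the conducted statistical results was considered at two tailed" alpha of .05) and names one method for the within-patient contrast: "The Wilcoxon Signed Ranks test was used to test paired differences in satisfaction ratings, dentist's evaluations, and OHIP-EDENT scores". For outcomes judged non-normal, which is every continuous variable except age and pre-treatment OHIP, "descriptive statistics for the non-normally distributed continuous variables included the mean, standard deviation, median, interquartile range, minimum value, and maximum value". No paired difference and no interval is named for the contrast. The Mann-Whitney test is planned in that section for comparisons between genders only.

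Table 1 follows this. Each denture has its own mean, SD, median, range and IQR, and the comparison columns hold only what the footnote describes: "Z= Z statistic using Wilcoxon signed ranks test, P= Two-tailed probability value". General satisfaction has a row for each denture but no Z or P.

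On retention at rest and during eating (both P=.052), the Results report a tendency in favour of carving and add: "This difference was not significant but was close to be significant". The OHIP result (P=.055) is also called a tendency, then said to be confirmed by a Mann-Whitney test of carved against non-carved (U=887.0, Z=-2.241, P=.025). Pain (P=.057) and dentist-rated stability (P=.057) are not discussed as carved versus non-carved results.

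Tables 6 and 7 do give a coefficient with a 95% interval for carving, on OHIP and on eight satisfaction outcomes.

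**The concern.** The carved versus non-carved contrast within patients is the question of this crossover trial. A Z and a P show how compatible the data are with no difference; they do not show how large the difference may be or how precisely it is known. A non-significant result from a narrow interval and one from a wide interval therefore look the same in Table 1 apart from the P value.

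Without an estimate to describe, what is said about a near-threshold result depends on choice of wording. Here two results at .052 and one at .055 are presented as leaning towards carving, while two at .057 get no comment. Nothing in the SAP sets a rule that separates them. At stake are the balance of the reported conclusions and the reader's ability to judge what the trial has and has not shown.

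**Working it through.** **Inputs.** Means, SDs, medians, Z and P: SAP Table 1. Carving coefficients, SEs and intervals: Tables 6 and 7. Number of patients: the Results give "The data was collected from a total of 49 participants (23 females and 27 males"), although 23 + 27 = 50 and the table titles say 50. The Table 2 counts add to 49 (for example 40 + 9), so 49 is used. The within-patient correlation r is not in the document and is an assumption.

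**1. The printed P values.** P = 2Φ(−|Z|).

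| Outcome | Z | P recomputed | P printed | Treatment in the Results |
|---|---|---|---|---|
| Retention at rest | -1.943 | .0520 | .052 | tendency, near significance |
| Retention during eating | -1.944 | .0519 | .052 | tendency, near significance |
| OHIP | -1.916 | .0554 | .055 | tendency, said to be confirmed |
| Dentist-rated stability | -1.906 | .0567 | .057 | none |
| Pain | -1.901 | .0573 | .057 | none |

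All 13 printed P values in Table 1 reproduce. The five above span Z from -1.901 to -1.944, a range of 0.043.

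**2. Can Table 1 supply the paired effect?** Medians are equal in 10 of the 14 carved/non-carved pairs: dentist retention, support and esthetics; pain, retention at rest, insertion, general satisfaction, eating, smile and speaking. They differ for dentist stability (8.5, 9.0), retention at function (7, 8), comfort (8, 9) and OHIP (9, 6). Means can be subtracted, but an interval needs r.

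**3. Can Tables 6 and 7 supply it?** For OHIP, the half-width is (1.107 + 3.755)/2 = 2.431, and 2.431/1.222 = 1.989. With 16 predictors, 49 rows leave 49 − 17 = 32 df (t = 2.037, half-width 2.489), which does not match. With 98 rows there are 81 df (t = 1.990, half-width 2.431), which matches; 100 rows match as well. So each patient enters twice, as if independent. The eight Table 7 intervals likewise match 98 to 100 rows to rounding, and not 49.

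The coefficients also estimate something other than the paired effect, because the models adjust for pain and dentist ratings recorded with the denture under test, and in Table 6 for satisfaction too:

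| Outcome | Raw mean difference, carved − non-carved | Regression B (95% CI) |
|---|---|---|
| OHIP | 8.45 − 11.12 = -2.67 | -1.324 (-3.755, 1.107) |
| Retention at rest | 8.67 − 8.06 = 0.61 | 0.338 (-0.447, 1.124) |
| Retention during eating | 7.98 − 7.25 = 0.73 | 0.454 (-0.351, 1.259) |

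Pain and the four dentist ratings are never outcomes in these models.

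**4. The Mann-Whitney test on OHIP.** With 49 against 49, the mean of U is 49 × 49/2 = 1200.5 and its SD is √(49 × 49 × 99/12) = 140.74. Z = (887 − 1200.5)/140.74 = -2.227, P = .026 without tie correction, against the printed -2.241 and .025. So the same patients' two scores were treated as two independent groups.

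**5. What an interval would add (illustration only).** SE = √(s₁² + s₂² − 2·r·s₁·s₂)/7; interval = difference ± 2.011·SE (48 df). For smile at r = 0.5: √(0.885² + 0.694² − 0.885 × 0.694)/7 = 0.115, giving 0.04 ± 0.23.

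| Outcome | Difference | r = 0 | r = 0.5 | r = 0.6 |
|---|---|---|---|---|
| Smile (P=.777) | 0.04 | (-0.28, 0.36) | (-0.19, 0.27) | (-0.17, 0.25) |
| Dentist retention (P=.175) | 0.32 | (-0.47, 1.11) | (-0.24, 0.88) | (-0.18, 0.82) |
| Retention at rest (P=.052) | 0.61 | (-0.27, 1.49) | (-0.02, 1.24) | (0.05, 1.17) |
| Pain (P=.057) | -0.88 | (-1.92, 0.16) | (-1.62, -0.14) | (-1.54, -0.22) |
| OHIP (P=.055) | -2.67 | (-5.57, 0.23) | (-4.74, -0.60) | (-4.53, -0.81) |

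At r = 0.5 the width is 0.27 + 0.19 = 0.46 for smile and 0.88 + 0.24 = 1.12 for dentist retention.

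**The case against.** Several points stand against a broader criticism.

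- A reader might infer that the document gives no estimate or interval for carving at all. It does: Tables 6 and 7 give both for nine outcomes. The gap is confined to the paired comparison, and those regressions do not fill it, for the reasons in the working.
- A reader might infer that all non-significant results carry a single label. They do not; Table 1 prints exact P values. But P values alone do not show precision.
- The sentence on P=.052 does say that the difference was not significant, so the .05 rule is softened in tone rather than broken. The OHIP passage goes further, because a paired result above .05 is said to be confirmed by an unpaired test that the SAP plans only for gender comparisons.
- Nothing shows that the missing estimate caused the tendency wording. The regression intervals were available when it was written.
- Table 1 agrees with the descriptives and the test that the SAP specifies, so this is a weakness of the chosen analysis and not an internal contradiction.
- The illustrative intervals use t methods on data that the SAP calls non-normal, with an assumed correlation. For rest, pain and OHIP, moving r from 0 to 0.6 takes the interval from including zero to excluding it.

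**Conclusion.** The point holds for the paired comparisons. Thirteen of the 14 carved/non-carved pairs have only Z and P, one has neither, and none has a paired difference with an interval. The regression intervals do not estimate the paired effect. Five results between P=.052 and P=.057 are described in three different ways without a stated rule.

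These conclusions rest on the printed tables. The finding of 98 to 100 regression rows is inferred from the interval widths. Only the illustrative intervals rest on assumptions (n = 49, r from 0 to 0.6, t-based). They show that precision differs between outcomes. A reader might take them as evidence that carving has an effect on pain or OHIP, or that an effect on smile is ruled out. They support neither: the answer changes with r, and the document states no margin for a relevant difference. It is a change that should be made to how the main contrast is estimated and reported; it does not overturn any printed P value.

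**What to change.** For every carved/non-carved pair, including general satisfaction, add to Table 1 the Hodges-Lehmann paired difference and the 95% interval obtained by inverting the signed-rank test, and name both in the Statistical analysis section. Add the missing Z and P for general satisfaction. Word all conclusions from the estimate and interval by one rule applied to every outcome. Delete the tendency and near-significance wording, and the statement that the Mann-Whitney test confirms the OHIP result.

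The cost is two columns and some rewording; the paired data are already held. There is a small downside. Many ratings are tied at the ceiling (insertion has an IQR of 0), so some estimates may be zero with coarse intervals, and the method assumes roughly symmetric differences. State both in a table note.
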